6.5.4. Anti-hypertensive Medications

Participants are permitted to receive stable doses of ARB or ACE inhibitors for the treatment of hypertension, cardiovascular disease, kidney disease, and LN. If receiving regular treatment with ACE inhibitors or ARBs, participants must be receiving stable dosing for at least 2 weeks prior to randomization. If necessary, participants are permitted to switch between ARB and ACE inhibitors or vice versa. Effort should be made to ensure that the effective doses of the switched drugs are comparable. The initiation of treatment with ARB or ACE inhibitors should be avoided between randomization and Week 52 unless other hypertensive treatments are contraindicated.

During the LTE, the dose of ACE inhibitors/ARBs may be changed or ACE inhibitors/ARBs may be initiated, if needed to help with blood pressure control or because of specific medication availability and/or convenience (eg, using combined ARB hydrochlorothiazide medications), but medication changes to treat LN flares would require discontinuation from the LTE.

6.5.5. Non-biologic Immunomodulators

Stable dosing of MMF or MPA as described in [Table 5](#) is required. No other immunomodulators are permitted during the study. A reduction in immunomodulators is allowed only if the participant develops unacceptable side effects, with the implication that this may affect interpretation of the participant’s clinical data. There should be no additions of a new immunomodulator to the existing treatment regimen.

For subjects who initiate MMF (or MPA) during screening or close to screening, the dose should be titrated up during screening based on tolerability to a target dose of ≤ 3.0 grams/day MMF (or equivalent MPA) and kept stable thereafter.

6.5.6. Topical Medications

Regular use of topical medications is permitted. “As needed” use of topical NSAIDs, analgesics, or other pain-relieving agents such as capsaicin is permitted, but not within 48 hours prior to study visit. “As needed” use of topical glucocorticoids is permitted if involving a limited BSA ($\leq 20\%$), but not within 48 hours prior to a study visit.

6.5.7. Prohibited Therapies

Use of additional immunosuppressants or immunomodulators, other than those explicitly allowed in the inclusion/exclusion criteria (Section [5.1](#) and [5.1.1](#)), are prohibited including, but not limited to, the following:

- Agents targeted at reducing TNF α (eg, infliximab, golimumab, certolizumab pegol, etanercept, CT-P13, adalimumab)
- B-cell targeted agents (anti-CD20 [eg, rituximab, obinutuzumab], anti-CD19 [eg, obexelimab (XmAb5871)], anti-B-cell activating factor, also known as B lymphocyte stimulator [BLyS; eg, belimumab], anti-CD22 [eg, inotuzumab, ozogamacin], or other B-cell targeted therapies, such as tabalumab, atacicept, daratumumab)
- IL-1 inhibitors (eg, canakinumab)
- IL-2 inhibitors or exogenous IL-2 therapy
- IFN inhibitors or exogenous IFN therapy
- IL-1 receptor antagonists (eg, anakinra)
- Tocilizumab or any other biologic targeting IL-6 or IL-6 receptor
- Tofacitinib, baricitinib, upadacitinib, or any other janus kinase inhibitor
- Abatacept
- Anti-IL-17 agents (eg, brodalumab, secukinumab, or ixekizumab)
- Leflunomide
- Cyclosporine A except for topical use
- Calcineurin inhibitors (eg, tacrolimus or pimecrolimus, voclosporin)
- Sirolimus, everolimus
- Immunomodulatory preparations (eg, MTX, AZA/6-MP, mizoribine)
- Toll-like receptor inhibitors
- Thalidomide or lenalidomide
- Dapsone
- ACTH by injection
- Epidural, IV, and IM glucocorticoids (see Section 6.5.2)
- Other investigational agents

Use of cytotoxic drugs is prohibited including, but not limited to, cyclophosphamide, chlorambucil, nitrogen mustard, or other alkylating agents.

Multiple administrations of high doses of oral glucocorticoids (average daily dose ≥ 60 mg), or initiation of high potency topical glucocorticoids ($>20\%$ BSA), are prohibited during the study as defined in Section 6.5.2.

Sulfa-based antibiotics, where reasonable and necessary, are allowed but should generally be avoided.

The use of complementary therapies (eg, herbs, ointments, traditional Chinese medicine, acupuncture) that have the potential to activate or inhibit the immune system is prohibited (see

Section 5.1.1). In addition, use of complementary therapies that have the potential to interact with antithrombotic agents is prohibited in those taking antithrombotic agents.

The use of other complementary therapies is strongly discouraged; in individual cases, use may be permitted following discussion with the study sponsor and/or medical monitor.

As these lists cannot be exhaustive, please consult the medical monitor to discuss prior to starting any biologic or other advanced therapies.

6.5.8. Rescue Medication

Higher doses of steroids can be used as rescue medication, however this may trigger a TF (see Section 6.5.2 for details on glucocorticoid therapy concomitant use).

Increases in doses of current medications or addition of new protocol permitted medications for SLE or LN disease activity, such as NSAIDs, ACE inhibitors, ARBs, immunomodulators (antimalarials) and, potentially, topically applied (>20% BSA) or locally injected therapies (if clinically indicated) should be discussed with the medical monitor and/or sponsor.

Severe, progressive, or unstable worsening of SLE disease activity that requires escalation in therapy, including biologics such as belimumab or rituximab, systemic immunomodulators such as cyclosporine or tacrolimus, sustained high doses of oral glucocorticoids, use of IV glucocorticoids, or use of cytotoxic agents such as cyclophosphamide may require discontinuation from the study intervention (see Section 6.5 and Section 7.1).

6.5.9. Vaccinations (including COVID-19)

When considering use of locally approved vaccines (including emergency use authorized COVID-19 vaccines) in study participants, follow applicable local vaccine labelling, guidelines, and standards of care for patients receiving immune-targeted therapy.

For study participants receiving a locally-approved COVID-19 vaccine (including emergency use authorized), in order to help identify acute reactions potentially related to COVID-19 vaccine, it is recommended where possible that vaccine and study drug be administered on different days, separated by as large an interval as is practical within the protocol.

6.6. Dose Modification

Not applicable.

6.7. Continued Access to Study Intervention After the End of the Study

Local regulations on continued access will always take precedence. Plans for continued access stated in this protocol may change if new information on the benefit-risk profile of guselkumab becomes available during the study or program.

At the end of their participation in the main study, participants who have completed the study and are benefiting from the study intervention, as determined by meeting CRR at Weeks 48 and 52, will be offered the opportunity to enter the LTE study.

If a DMC review performed prior to the first patient's entry into the LTE or during the LTE demonstrates unfavorable benefit:risk profile or safety concerns arise, the study (and LTE) may be stopped.

7. DISCONTINUATION OF STUDY INTERVENTION AND PARTICIPANT DISCONTINUATION/WITHDRAWAL

7.1. Discontinuation of Study Intervention

A participant's study intervention must be discontinued if:

- The participant withdraws consent to receive study intervention.
- The investigator believes that for safety reasons or tolerability reasons (eg, AEs) it is in the best interest of the participant to discontinue study intervention.
- The participant becomes pregnant within the study period. Refer to Appendix 5 [Section 10.5], Contraceptive Guidance and Collection of Pregnancy Information.
- The participant develops an opportunistic infection (this does not include candidiasis that is limited to the mouth).
- The participant is deemed ineligible according to the following TB screening criteria:

A diagnosis of active TB is made.

A participant has symptoms suggestive of active TB based on follow-up assessment questions and/or physical examination, or has had recent close contact with a person with active TB, and cannot or will not continue to undergo additional evaluation.

A participant undergoing evaluation has a chest radiograph with evidence of current active TB and/or a positive QuantiFERON-TB[®] test result (and/or a positive tuberculin skin test result in countries in which the QuantiFERON-TB[®] test is not approved/registered or the tuberculin skin test is mandated by local health authorities), unless active TB can be ruled out and appropriate treatment for latent TB can be initiated prior to the next study intervention administration and continued to completion (see also Section 8.2.11 and Appendix 3 [Section 10.3]). Indeterminate QuantiFERON-TB[®] test results should be handled as described in Section 8.2.11. Participants with persistently indeterminate QuantiFERON-TB[®] test results may continue without treatment for latent TB if active TB is ruled out, their chest radiograph shows no abnormality suggestive of TB (active or old, inactive TB) and the participant has no additional risk factors for TB as determined by the investigator. This determination must be promptly reported to the medical monitor or designee and recorded in the participant's source documents and initialed by the investigator.

Note: In Ukraine, while the QuantiFERON-TB[®] test is not approved/registered, it is acceptable, and an additional tuberculin skin test is not required.

A participant receiving treatment for latent TB discontinues this treatment prematurely or is noncompliant with the therapy.

- The participant has a serious adverse reaction that is related to an injection or an infusion resulting in bronchospasm with wheezing and/or dyspnea that requires ventilatory support OR that results in symptomatic hypotension with a decrease in systolic blood pressure >40 mm Hg or blood pressure <90/60 mm Hg.
- The participant has a reaction resulting in myalgia and/or arthralgia with fever and/or rash (suggestive of serum sickness and not representative of signs and symptoms of other recognized clinical syndromes) occurring 1 to 14 days after an injection of study intervention. These may be accompanied by other events including pruritus, facial, hand, or lip edema, dysphagia, urticaria, sore throat, and/or headache.
- The participant has a malignancy including squamous cell skin cancer. Consideration may be given to allowing participants who develop ≤ 2 basal cell skin cancers that are adequately treated with no evidence of residual disease to continue to receive study intervention.
- Participant requires dialysis.
- Noncompliance with study drug administration defined as multiple episodes of missing the window in which to receive study intervention.
- The participant has severe liver test abnormalities that meet one of the conditions outlined in Appendix 11 (Section 10.11; Liver Safety: Suggested Actions and Follow-up Assessments).

The sponsor may elect to terminate the study at any time, and if the sponsor decides not to continue development for any reason, study medication/drug will no longer be provided to any participants, including those in the LTE.

Discontinuation of a participant's study intervention should be considered under the following conditions:

1. Persistent inadequate response or worsening of LN based on worsening of renal function.
2. If the participant initiates treatment with prohibited therapies for SLE or LN, the medical monitor or designee should be notified for possible discontinuation of study intervention (Section 6.5).
3. The participant develops a serious infection, including but not limited to sepsis or pneumonia.
Note: Any serious infection should be discussed with the medical monitor or designee, and study intervention should be withheld until the clinical assessment is complete.
4. Discontinuation of study treatment should be considered for participants who report suicidal Ideation level 4 (some intent to act, no plan), Ideation level 5 (specific plan and intent), or any suicidal behavior (actual suicide attempts, interrupted attempts, aborted attempts, or preparatory actions) on a postbaseline (after Week 0) eC-SSRS assessment. Discussion of such subjects with the medical monitor or designee is required.
5. The participant develops a severe injection-site or infusion reaction, but not meeting criteria specified above.

If a participant discontinues study intervention for any reason before the end of the double-blind phase they may continue in the study. If the participant wishes to discontinue the study, then the Final Efficacy Visit and final safety visit assessments should be obtained as specified in the SoA

(Section 1.3, or as noted in Footnote c of the SoA). Study intervention assigned to the participant who discontinued study intervention may not be assigned to another participant.

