	
Infections have been identified as adverse reactions of guselkumab, including respiratory infections, herpes simplex and tinea infections, and gastroenteritis.
	
HCV), will be excluded from the study. Similarly, participants with evidence of active or untreated latent tuberculosis (TB) will be excluded from the study (Section 5.1.1).
 
 • Participants who have received a live viral or bacterial vaccination within 12 weeks of baseline will be excluded from the study. In addition, participants must agree not to receive a live viral or live bacterial vaccination during the study and for 12 weeks after receiving the last dose of study intervention (Section 5.1.1). • Participants will be instructed to seek medical attention if they develop signs or symptoms suggestive of an infection, and investigators are instructed in the protocol to monitor for signs or symptoms of infections, including TB (Sections 8.2.10 and 8.2.11). • Discontinuation of a participant’s study intervention must be strongly considered if the participant develops a serious infection, including but not limited to sepsis or pneumonia. In addition, any serious infection should be discussed with the medical monitor or designee, and study intervention should be withheld until the clinical assessment is complete (Section 7.1).

Hypersensitivity reactions, including serious hypersensitivity reactions.
	
Serious hypersensitivity reactions including anaphylaxis have been reported in postmarketing experience with guselkumab in psoriasis patients.
 
Hypersensitivity, including anaphylaxis, urticaria and rash have been identified as adverse drug reactions for guselkumab.
	
 • Participants with known allergy, hypersensitivity, or intolerance to guselkumab or its excipients will be excluded from the study. • Sites are instructed that before any administration of study intervention, appropriately trained personnel and medications (eg, injectable epinephrine) must be available to treat hypersensitivity reactions, including anaphylaxis. In addition, all participants must be observed carefully for signs and symptoms of a hypersensitivity reaction (eg, urticaria, pruritis, angioedema, wheezing, dyspnea, or hypotension) (Section 8.2.8). • Any participant who develops a serious hypersensitivity reaction such as anaphylaxis must discontinue study intervention (Section 7.1).

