10.10.1. Adverse Event Definitions and Classifications

Adverse Event

An adverse event (AE) is any untoward medical occurrence in a clinical study participant administered a pharmaceutical (investigational or non-investigational) product. An AE does not necessarily have a causal relationship with the intervention. An AE can therefore be any unfavorable and unintended sign (including an abnormal finding), symptom, or disease temporally associated with the use of a medicinal (investigational or non-investigational) product, whether or not related to that medicinal (investigational or non-investigational) product. (Definition per International Conference on Harmonisation [ICH])

This includes any occurrence that is new in onset or aggravated in severity or frequency from the baseline condition, or abnormal results of diagnostic procedures, including laboratory test abnormalities.

Note: The sponsor collects adverse events (AEs) starting with the signing of the ICF (refer to All Adverse Events under Section 8.3.1, Time Period and Frequency for Collecting Adverse Events and Serious Adverse Events Information, for time of last adverse event recording).

For combination products with a device constituent, AEs include those resulting from insufficient or inadequate instructions for use, deployment, implantation, installation, or operation, or any malfunction of the device. It includes any adverse event resulting from use error or from intentional misuse of the investigational device.

Serious Adverse Event

A serious adverse event (SAE) based on ICH and EU Guidelines on Pharmacovigilance for Medicinal Products for Human Use is any untoward medical occurrence that at any dose:

- Results in death
- Is life-threatening
(The participant was at risk of death at the time of the event. It does not refer to an event that hypothetically might have caused death if it were more severe.)
- Requires inpatient hospitalization or prolongation of existing hospitalization
- Results in persistent or significant disability/incapacity
- Is a congenital anomaly/birth defect
- Is a suspected transmission of any infectious agent via a medicinal product
- Is Medically Important*

*Medical and scientific judgment should be exercised in deciding whether expedited reporting is also appropriate in other situations, such as important medical events that may not be immediately

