10.11. Appendix 11: Liver Safety: Suggested Actions and Follow-up Assessments

10.11.1. Stopping Algorithm

Study intervention will be discontinued for a participant if liver chemistry stopping criteria are met.

Phase 2 Liver Chemistry Stopping Criteria and Increased Monitoring Algorithm (no preexisting liver disease)

10.11.2. Follow-up Assessments**10.11.2.1. Phase 2 Liver Chemistry Stopping Criteria and Follow-up Assessments**

Phase 2 liver chemistry stopping criteria are designed to assure participant safety and to evaluate liver event etiology.

Liver Chemistry Stopping Criteria	
ALT/AST--absolute	ALT or AST- $\geq 5 \times \text{ULN}$
ALT/AST-Increase	
If cannot monitor: ALT or AST- $\geq 3 \times \text{ULN}$ and cannot be monitored weekly for 4 weeks
 
Or if able to monitor: ALT or AST- $\geq 3 \times \text{ULN}$ persists for ≥ 4 weeks

Total bilirubin^{1, 2}	ALT or AST- $\geq 3 \times \text{ULN}$ and total bilirubin $\geq 2 \times \text{ULN}$ (or at least a doubling of direct bilirubin in known Gilbert's syndrome)
INR²	ALT or AST- $\geq 3 \times \text{ULN}$ and international normalized ratio (INR) > 1.5 , if INR measured
Symptomatic³	ALT or AST- $\geq 3 \times \text{ULN}$ associated with symptoms (new or worsening) believed to be related to liver injury or hypersensitivity
Suggested Actions, Monitoring and Follow-up Assessments	
Actions	Follow-up Assessments

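### Section 2.3.1 makes stopping mandatory after any serious hypersensitivity reaction and cites Section 7.1, but no mandatory criterion in 7.1 has that scope

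*Protocol*

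**What the plan says.** Protocol Section 2.3.1 lists hypersensitivity among the risks of the study drug and states: "Hypersensitivity, including anaphylaxis, urticaria and rash have been identified as adverse drug reactions for guselkumab". Its mitigation column sets the rule: "Any participant who develops a serious hypersensitivity reaction such as anaphylaxis must discontinue study intervention (Section 7.1").

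Section 7.1 contains two lists. The first gives the conditions under which study intervention must stop. Four of its bullets bear on this point:

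- A serious reaction related to an injection or infusion that involves "bronchospasm with wheezing and/or dyspnea that requires ventilatory support OR that results in symptomatic hypotension". The hypotension is defined as a systolic fall of more than 40 mm Hg or a pressure below 90/60 mm Hg.
- "The participant has a reaction resulting in myalgia and/or arthralgia with fever and/or rash (suggestive of serum sickness"), with onset 1 to 14 days after an injection.
- Liver test abnormalities meeting Appendix 11 (Section 10.11). One criterion there is ALT or AST at or above 3 times the upper limit of normal "associated with symptoms (new or worsening) believed to be related to liver injury or hypersensitivity".
- A general bullet that applies when "The investigator believes that for safety reasons or tolerability reasons (eg, AEs) it is in the best interest of the participant" to stop.

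The second list gives conditions under which a stop is only to be considered. Item 5 reads: "The participant develops a severe injection-site or infusion reaction, but not meeting criteria specified above".

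**The concern.** Section 2.3.1 removes discretion for every serious hypersensitivity reaction. The section it cites restores discretion for some of them. Sites look to 7.1 for stopping criteria, so a site working from that list could give another dose after a reaction for which 2.3.1 requires a stop.

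That is unlikely to be intended. Exclusion criterion 48 in Section 5.2 keeps out anyone with a previous immediate hypersensitivity response to a monoclonal antibody, so optional re-dosing after such a response on study would contradict the entry rule.

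The mismatch also reaches the long-term extension, because Section 7.1.1 applies the 7.1 criteria there. Section 4.1.2 allows home dosing in the extension, whereas the Section 8.2.8 requirement for trained staff and epinephrine applies to dosing at the study site.

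**Working it through.** No formula applies. The check is a count and a comparison of texts.

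**Count of mandatory bullets in 7.1.** They are: withdrawn consent, best interest, pregnancy, opportunistic infection, tuberculosis criteria (5); then acute injection or infusion reaction, serum-sickness-like reaction, malignancy, dialysis, noncompliance, liver tests (6). Total 5 + 6 = 11.

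- Naming hypersensitivity or anaphylaxis: 0 of 11.
- Catching particular forms: 3 of 11 (acute reaction, serum-sickness-like reaction, liver criteria).
- Resting on the investigator's best-interest judgement: 1 of 11.

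**Test case.** Within an hour of dosing a participant develops generalised urticaria and angioedema, is given epinephrine and is admitted overnight. There is no bronchospasm, dyspnea, fever, myalgia or arthralgia, and blood pressure and liver tests are normal.

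1. *Is it hypersensitivity?* Yes. Section 8.2.8 lists urticaria and angioedema among the signs.
2. *Is it serious?* Yes, by this criterion in Section 10.10.1: "Requires inpatient hospitalization or prolongation of existing hospitalization".
3. *Section 2.3.1:* dosing must stop.
4. *Section 7.1, mandatory list:* the acute-reaction bullet fails (no bronchospasm, no qualifying hypotension). The serum-sickness bullet fails (no myalgia or arthralgia, and onset is too early). The liver bullet fails (normal tests). Only the best-interest bullet remains, and it binds only once the investigator has reached that view.
5. *Section 7.1, second list:* after an infusion, item 5 applies if the reaction is severe, and a stop is only to be considered. After a subcutaneous dose, item 5 covers injection-site reactions, which Section 8.2.7 defines as reactions at the site itself, so a systemic reaction falls outside it.

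The wording of the acute-reaction bullet leaves open whether the need for ventilatory support qualifies bronchospasm as well as dyspnea. The test case has neither, so the result does not depend on that reading.

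**Is the rule elsewhere?** Section 8.2.8 gives no stopping rule. Section 8.2.9 deals with managing and restarting an interrupted infusion and says nothing about later doses.

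**Omission or choice?** The other risks in 2.3.1 that cite 7.1 have a counterpart there: worsening nephritis or prohibited therapy (best-interest bullet, items 1 and 2), serious infection (item 3), malignancy and liver injury (mandatory bullets). Hypersensitivity is the one whose stated scope is missing.

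**The case against.** The strongest reply is that the two sections do not truly conflict. Section 7.1 does not claim to be exhaustive and nowhere permits dosing after a serious hypersensitivity reaction, so a site that stops complies with both. Section 7.1 is not the only source of mandatory stops either: a nephritis flare in the main study requires one under Sections 4.1.1 and 6.5, yet has no mandatory bullet of its own in 7.1. This is correct, but it does not settle the matter. For infusion reactions 7.1 is not merely silent: item 5 assigns a weaker instruction to those that miss the specific criteria.

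Second, the most dangerous anaphylaxis is already caught, and other controls apply. Serious events go to the sponsor within 24 hours (Section 8.3.1) and to the data monitoring committee on an ongoing basis (SAP Section 5.9.2). Extension participants are told to report signs of allergic reaction promptly (Section 4.1.2), and home dosing begins only after training. All of this stands and lowers the risk. None of it makes the stop mandatory in the test case. Whether epinephrine is available at home is a separate question.

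Third, since 2.3.1 already requires the stop, a protocol clarification communication might seem enough. Section 10.9.1 allows one for unclear wording that leaves study conduct unchanged, but says it must not take the place of an amendment. Adding a stopping criterion and narrowing item 5 changes the text of a stopping rule, which is amendment material.

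Fourth, the study is closing. That limits exposure, but dosing continues until all enrolled participants complete Week 20.

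**Conclusion.** The concern holds. On the current protocol text, 2.3.1 requires a stop for every serious hypersensitivity reaction, while 7.1 requires it for particular forms and leaves the rest to judgement. The rule does exist in the protocol; the fault is that the section cited for it is weaker.

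The gap concerns acute serious reactions without bronchospasm or dyspnea and without qualifying hypotension. Its clinical size cannot be given, because the documents state no event frequency. Exposure is limited by the end of screening and the planned end of dosing in Section 4.1.1. Sample size, error rate and analysis are unaffected. It should be fixed because it is a safety instruction on an identified adverse reaction and the correction is small. The conclusion assumes that sites take their stopping criteria mainly from 7.1, as the citation in 2.3.1 directs.

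**What to change.** By protocol amendment, make two changes in Section 7.1:

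- Add a bullet to the mandatory list: *the participant has a serious hypersensitivity reaction, including anaphylaxis*.
- Limit item 5 of the second list to severe injection-site or infusion reactions that are not serious hypersensitivity reactions.

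Section 7.1.1 then carries the rule into the extension, and the citation in 2.3.1 becomes correct without any edit there. The cost is one bullet, one limiting clause, and the formal amendment with ethics committee approval that Section 10.9.1 requires. No procedure, visit or data item is added, and the stop itself is already required by 2.3.1.
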